### 10.4.4 Baseline Descriptive Statistics

We will compare quality improvement program cohorts based on baseline demographic variables including age, sex, education, race, ethnicity, healthcare literacy, functional status, and comorbidities using descriptive statistics and t-tests.

### 10.4.5 Planned Interim Analysis

See. [10.4.2](#)

CONFIDENTIAL

This material is the property of the NYU School of Medicine and Langone Medical Center. Do not disclose or use except as authorized in writing by the study sponsor  
 Interventional Template Version: 28 APR 2017

#### 10.4.5.1 Safety Review

See [8.7](#) and [10.4.2](#).

#### 10.4.5.2 Efficacy Review

See [10.4.2](#). Efficacy will not be considered in halting the study.

### 10.4.6 Additional Sub-Group Analyses

We will perform sub-group analyses based on age, sex, and race/ethnicity. We will perform both descriptive and multivariate comparisons.

### 10.4.7 Multiple Comparison/Multiplicity

Not Applicable

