## Protocol Summary

Title	A Multisite cluster RCT of the dementia symptom management at home program
Brief Summary	Alzheimer's Disease and Related Disorders (dementia) poses a significant challenge to our public health. While many persons with dementia are cared for by friends and family in the community with the assistance of home healthcare, most home healthcare clinicians and agencies are ill prepared to care for this population and therefore have difficulty assisting patients and caregivers in maintaining quality of life leading to adverse patient outcomes, increased caregiver stress and burnout, and healthcare utilization. This study will therefore utilize a cluster randomized controlled design at 3 study sites to examine the ability of a multi-component evidence-based practice primary palliative care quality improvement program for home healthcare registered nurses, occupational therapists and physical therapists to improve the quality of life and reduce healthcare utilization for persons with dementia and their informal caregiver.
Phase	3
Objectives	
1) Measure the effects of the DSM-H on quality of life (primary) and pain and BPSD severity (secondary) in the PWD.
 
2) Assess the effects of the DSM-H on quality of life (primary), and physical and mental health (secondary) in the informal caregiver of the PWD.
 
3) Assess the effects of the DSM-H on healthcare utilization in the PWD. Primary outcomes are ER visits and hospital admission rates. Secondary outcomes are outpatient visits and primary care provider contacts.

Methodology	Multi-site cluster randomized controlled trial of a quality improvement program
Endpoint	
Primary Endpoints: PWD and caregiver QOL. Number of PWD ER visits and inpatient admissions
 
Secondary Endpoints: PWD Pain and severity of individual BPSD, antipsychotic and analgesic use. PWD outpatient visits and primary care provider contacts. Caregiver burden, depression, functional health and well-being.

Study Duration	3.75 years
Participant Duration	60 days

CONFIDENTIAL

This material is the property of the NYU School of Medicine and Langone Medical Center. Do not disclose or use except as authorized in writing by the study sponsor

Interventional Template Version: 28 APR 2017

[figure not shown]

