***Aim 3: Assess the effects of the DSM-H on healthcare utilization in the PWD.***

H3: PWD cared for by a HHC team utilizing the DSM-H performance improvement program will show a reduction in emergency room visits and hospital admissions compared to the control (usual care) group, and a greater number of outpatient visits.

The primary outcomes to be measured are the number of emergency room visits and hospital admission rates of the PWD at 30 and 60 days. It will be measured through interviews with the informal caregiver using the Resource Utilization Inventory.

CONFIDENTIAL

This material is the property of the NYU School of Medicine and Langone Medical Center. Do not disclose or use except as authorized in writing by the study sponsor  
 Interventional Template Version: 28 APR 2017

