### **4.2 Study Endpoints**

#### **4.2.1 Primary Study Endpoints**

Given that this is a dyadic, implementation science intervention, it is not appropriate to look at a single primary endpoint. There are therefore 3 primary endpoints that will be examined in this study. For the Aim 1 primary endpoint, PWD QOL, a 0.5 SD difference between the baseline and 60 day visit would be clinically meaningful based on prior studies and therefore considered a positive outcome. For the Aim 2 primary

CONFIDENTIAL

This material is the property of the NYU School of Medicine and Langone Medical Center. Do not disclose or use except as authorized in writing by the study sponsor  
 Interventional Template Version: 28 APR 2017

endpoint, informal caregiver QOL, given its rate of variability and floor and ceiling effects, a 0.5 SD difference between the baseline and 60 day visit would be clinically meaningful and therefore considered a positive outcome. For the Aim 3 primary endpoint, a 10% reduction in readmissions and ER visits at 60 days will be considered a clinically meaningful positive outcome. This would result in 220 fewer ER visits and 63.8 fewer admissions per 1000 patients based on prior evidence.

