#### 4.2.2 Secondary Study Endpoints

Aim 1 secondary endpoints include individual BPSDs, pain, antipsychotic use and analgesic use. These endpoints were chosen secondary to their relationship to QOL and caregiver QOL as noted above in sections [2.1.1](#) and [2.1.2](#) as well as their interrelationship as noted in [section 2.1.3](#).

Aim 2 secondary endpoints include informal caregiver burden, depression, and health, which as noted in section [2.1.4](#).

Aim 3 secondary endpoints include outpatient visits and primary care provider contacts. These endpoints are included as BPSDs and pain are both indicators of additional concerns amongst caregivers and can increase burden due to the coordination that is required of caregivers.

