## **7 Study Procedures and Schedule**

### **7.1 Study Procedures/Evaluations**

#### **7.1.1 Study Specific Procedures**

All data will be collected virtually via telephone and through internet capabilities. The following questionnaires will be collected by the research team as part of research assessment of efficacy of the intervention as it relates to the aims for both performance improvement and control subjects:

- Quick Dementia Rating Scale (QDRS): Is a 10-item tool that measures cognitive impairment based on the severity of dementia.
- Neuropsychiatric Inventory Questionnaire (NPI-Q): Is a 13-item tool that measures caregiver perceptions of dementia BPSD presence and severity.
- Quality of Life in Alzheimer's Disease (QOL-AD): Is a 13-item tool that measures caregiver perceptions of quality of life in the PWD
- PAINAD: Is a pain assessment tool for use in persons with moderate to severe dementia who cannot provide reliable report.
- Brief Pain Inventory Short Form (BPI) is a 9-item tool that measures pain location, severity and intensity.
- FAM-CAM: Is an 11-item tool that is an informant-based assessment of delirium.
- Medication Record and use: We will create a list of medications the PWD is taking as well as the frequency of administration of any PRN medications taken, including any OTC or herbal supplements. The primary reason for collecting this data is to examine analgesic and antipsychotic use.
- Caregiver Targeted Quality of Life Tool (CGQOL): Is an 80-item tool with 10 domains for measuring the quality of life of the caregiver of the PWD.
- Public Health Questionnaire 9 (PHQ-9): Is a 9-item tool that measures depressive symptoms.
- Zarit Burden Inventory: Is a 22-item tool that measures caregiver burden.
- SF-12: The SF-12 is a 12-item tool that measures functional health and well-being.
- ADLs and IADLS: Are 12 items that measure functional status as part of the QOL-AD.
- Charlson Comorbidity Index: Is a reliable and valid comorbidity assessment tool.
- The Short Assessment of Health Literacy (SAHL): Is an 18-item test designed to examine health literacy levels
- Other non-instrumented questions that will be asked include sociodemographics (DOB, sex, highest education level attained, race, ethnicity, primary language, religion, marital status, household members, number type and frequency of unpaid and paid caregivers, and primary care provider name and contact for both PWD and caregiver.

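### Section 10.4.7 sets multiplicity aside although three primary endpoints are each judged positive on their own and the BPSD endpoint is individual NPI-Q symptoms, so nothing limits error across either family

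*Combined protocol and SAP*

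**What the plan says.** Section 10.4.7 (Multiple Comparison/Multiplicity) consists of "Not Applicable". Section 10.1 says that no formal SAP will be written, so section 10 is the only place for an error-rate rule.

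Section 4.2.1 rejects a single primary endpoint: "There are therefore 3 primary endpoints that will be examined in this study". Each has its own threshold: 0.5 SD for PWD quality of life, 0.5 SD for caregiver quality of life and, for Aim 3, "a 10% reduction in readmissions and ER visits at 60 days will be considered a clinically meaningful positive outcome". The section gives no joint success rule.

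Section 4.2.2 lists the secondary endpoints: "Aim 1 secondary endpoints include individual BPSDs, pain, antipsychotic use and analgesic use". BPSD is measured with the NPI-Q, which section 7.1.1 describes thus: "Is a 13-item tool that measures caregiver perceptions of dementia BPSD presence and severity". Section 10.4.1 applies a mixed model to primary and secondary outcomes alike and gives no significance level.

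An alpha of .05 appears in two places: the QOL-AD sample-size calculation (10.5) and the interim safety tests (10.4.2).

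The Aim 3 primary outcome is described inconsistently. The Protocol Summary has "Primary Endpoints: PWD and caregiver QOL. Number of PWD ER visits and inpatient admissions". Section 3.1 has "number of emergency room visits and hospital admission rates of the PWD at 30 and 60 days". Section 10.4.1 lists only emergency room visits among the primary outcomes and puts hospital admissions under secondary. It plans logistic and Poisson models for both kinds of event, at 30 and 60 days.

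**The concern.** Multiplicity does apply to this design. There are at least three primary comparisons, all bearing on one program, and one secondary endpoint that is itself a set of symptoms. With no order, no division of alpha and no requirement that all succeed, whichever endpoint, timepoint or model falls below .05 could be presented as evidence that the DSM-H works. Section 2.5.1 links a finding of efficacy to dissemination among home healthcare agencies, so the claim has consequences beyond a single aim.

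**Working it through.** **Inputs.** Three primary endpoints (4.2.1); 13 NPI-Q items (7.1.1); alpha .05, power .80, ICC .05, 20 clusters of 15 dyads, 10 clusters per arm, covariates explaining 15% of variance (10.5). Two-sided testing is assumed, because the protocol does not state sidedness for efficacy. The documents give no correlations between outcomes, so those below are assumptions.

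**1. Reproducing the plan's own figure.**
- Variance of the standardised difference: 4 × (ICC + (1 − ICC)/n)/J = 4 × (.05 + .95/15)/20 = .02267, so SE = .1506.
- Non-central t with 18 df at two-sided .05, no covariates: power at .45 is .807, and the detectable effect at .80 power is .446. The stated .45 is therefore reproduced as one test at .05.

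**2. Error across each family at .05 per test.**
- Independent, either direction: 1 − .95³ = .143; 1 − .95¹³ = .487.
- Independent, improvement only (.025 per test): 1 − .975³ = .073; 1 − .975¹³ = .280.
- Correlated: equicorrelated normal test statistics.

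| Family | Assumed correlation | At least one false result, either direction | At least one false improvement |
|---|---|---|---|
| 3 primaries | 0 | 14.3% | 7.3% |
| 3 primaries | .5 | 12.5% | about 6% |
| 13 NPI-Q items | 0 | 48.7% | 28% |
| 13 NPI-Q items | .3 | 42% | 21% |
| 13 NPI-Q items | .5 | 33% | 17% |
| One test, for reference | – | 5% | 2.5% |

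Even at correlation .9 the either-direction rates are about 8% and 14%. If emergency visits and admissions are counted as separate primaries, making four, the independent either-direction figure is 1 − .95⁴ = 18.5%.

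**3. Cost of control for QOL-AD.** The strictest step of Holm or Hochberg with three tests is .05/3 = .0167 (critical t 2.639 on 18 df). If covariates remove 15% of total variance, SE = .1506 × √.85 = .1388.

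| | Detectable effect at .80 power | Power at .45 | Power at 0.5 SD |
|---|---|---|---|
| .05, no covariates | .446 | .81 | .88 |
| .0167, no covariates | .53 | .64 | .745 |
| .0167, 15% of total variance removed | .49 | .72 | .82 |

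If the 15% applies only to the between-cluster variance, the .0167 row becomes .51, .67 and .78. Holding .80 power at .45 with alpha .0167 would take about 28 clusters (420 completed dyads) without covariates, or 24 (360) with 15% of total variance removed.

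**The case against.** The strongest reply is that the three aims concern different outcomes, partly in different people, and that whether separately stated hypotheses need joint control is partly convention. Section 4.2.1 argues for several primaries, and its criteria are effect sizes rather than p-values. That reply could be defended, but the protocol does not make it. Declaring the topic inapplicable neither confines claims to single aims nor gives a reason for having no control.

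Three parts of the opposing case stand and limit the point.
- A reader might infer that any one positive endpoint makes the trial positive, or that .05 is claimed as a trial-wide level. The documents say neither. Each result is judged for its own aim, and the .05 in 10.5 is valid for its single QOL-AD test.
- A reader might infer a near-even chance of falsely reporting that some behaviour improved. The 48.7% counts errors in both directions; false improvement is 28% at most under the two-sided assumption. H1 to H3 are directional, so the smaller figure bears on a benefit claim.
- A reader might infer that 13 significance tests are specified. They are not: item-by-item testing follows from the individual-symptom endpoint and the item count. BPSD is secondary, so lack of control matters mainly if single symptoms are presented as confirmatory.

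The power cost is also real, and because 10.5 gives no power for Aims 2 and 3, the cost for those aims cannot be computed from the documents.

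**Conclusion.** The point holds. The entry in 10.4.7 is wrong for this design and is not merely a missing detail. The protocol has no family-level protection for its primary endpoints or for the individual symptoms. For three primaries the chance of a false improvement on at least one is about 6% to 7%, roughly two and a half to three times the 2.5% of a single test. For the NPI-Q items it is 17% to 28% over correlations from .5 to 0.

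These figures assume two-sided .05 per test, the stated correlations, no true effect on any outcome in the family and, for the symptoms, a separate test of all 13 items. They describe what happens if any single nominal result is used to claim benefit. The protocol does not state such a rule, but it does not exclude one.

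**What to change.** 1. Reconcile the Aim 3 primary outcome between the Protocol Summary, 3.1, 4.2.1 and 10.4.1 (emergency visits, admissions or both; 30 or 60 days; logistic or Poisson). Then name one deciding test per aim. No alpha rule can be written before this is done.
2. Replace the entry in 10.4.7 with Holm or Hochberg across the three deciding tests, at overall two-sided .05, for any claim that the DSM-H is effective. Neither does worse than Bonferroni.
3. For the NPI-Q items, apply Holm or false-discovery-rate control, or state that they are descriptive and reported with intervals only.
4. Restate 10.5 with the figures at .0167: detectable effect .53 without covariates, or .49 if covariates remove 15% of total variance; power .64 (.72) at .45 and .745 (.82) at 0.5 SD. State how the 15% is assumed to act.

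The cost is wording and analysis work; no more dyads are proposed. The downside is lower power at .45 under the strictest step. With the 15% covariate assumption on total variance, power at the 0.5 SD that the protocol calls meaningful stays above .80; without covariates it does not.

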### 10.4.8 Tabulation of Individual Response Data

Individual participant data will not be listed, with the exception of spaghetti plots of change over time.

### 10.4.9 Exploratory Analyses

We will examine the effect of ADL function on non-QOL outcomes. We will also examine the interaction of caregiver and PWD primary and secondary outcomes.

## 10.5 Sample Size

Power analyses were conducted using Optimal Design software. Given that this study is randomized at the cluster level, we must control for intra-class correlation, and have therefore calculated all power with an intra-class coefficient of .05, which is more conservative than the most recent clustered palliative care study and aligns well with prior community-based cluster trials. The Quality of Life in Alzheimer's Disease as the primary outcome measure in aim 1 has an average score of 33.1, standard deviation of 5.9. A .5 standard deviation difference in this measure would be clinically meaningful. Therefore, in a 2-sample comparison with a power of .80, an alpha of .05 and covariates that account for a cumulative 15% of the variance in outcome would require 15 dyads per cluster, and 20 clusters (10 per arm) at 60 days to detect a medium effect ( $\delta = .45$ ). For mixed effects linear models, the projected sample size will also allow us to detect a medium linear treatment effect ( $\delta = .45$ ) between groups in unadjusted analyses (assuming 15 dyads per cluster, 20 clusters, 4 observations, and an ICC = .05). Although there are no closed-form equations for calculating the power of linear models that include covariates, any non-zero correlation between covariates and the outcome will reduce the unexplained (error) variance thus increasing the statistical power of our tests, and reducing the minimum detectable effect size. As such, the detectable effect size estimated for the unadjusted analyses can be considered an upper bound estimate for the effect size detectable in adjusted analyses. **We will recruit until we have reached 15 completed cases in each cluster (N=300).** Conservatively anticipating a 15% dropout over the 60 days requires a **total recruitment goal of 345 dyads**. As almost 20,000 patients are seen each year in the three HHC agencies in this study, approximately 30% with ADRD, we do not expect any difficulty recruiting this sample, even with an unanticipatedly high rate of dyads declining to participate.

In addition, for fidelity monitoring, as discussed in section [6.1.6.1](#), we will consent **300 clinicians** at the participating HHC agencies on usual care and quality improvement care teams to complete fidelity monitor by performing the DSKA survey. These clinicians are not study subjects but will be consented as they are

CONFIDENTIAL

This material is the property of the NYU School of Medicine and Langone Medical Center. Do not disclose or use except as authorized in writing by the study sponsor

performing these surveys to assist the research team in monitoring fidelity of the quality improvement program.

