Population	
Dyad Population
 
Total Sample: 345 Dyads (345 PWD + 345 caregivers)  Sample at NYU Site (VNAHG): 207  Sample at University of Utah Site (CNS; Central Utah): 86  Sample at University of Miami Site (FirstStat; Southern Florida): 52  Sample Description: PWD and their informal caregiver dyads. PWD must be 65 or older and informal caregiver 18 or over; English or Spanish speaking; Informal caregiver is defined as spending at least 8 hours per week and had an established prior relationship (family, friend, neighbor).

Study Sites	
NYU (lead): 0 clusters  VNAHG: 12 clusters  University of Utah: 5 clusters  University of Miami: 3 clusters

Number of participants	
Dyads: 345 across all sites (see population)

Description of Study Procedure	
The DSM-H is a multi-component quality improvement program that consists of clinician training, patient- and family-centered assessment instruments, patient-caregiver dyadic centered care plans, a BPSD assessment and treatment algorithm, and caregiver teaching sheets. This study will examine outcomes of this quality improvement program.

Reference Therapy	
Usual Care

Key Procedures	
None

Statistical Analysis	
Time trend analysis using repeated measure multivariate mixed effects linear models (PROC MCM in SAS) for all non-utilization outcomes. Utilization outcomes will be analyzed through logistic regression for odds of hospitalization or ER visit and Poisson Count regression for total number of hospitalizations and ER visits. Both will use random effects to measure for clustering.

CONFIDENTIAL

This material is the property of the NYU School of Medicine and Langone Medical Center. Do not disclose or use except as authorized in writing by the study sponsor

Interventional Template Version: 28 APR 2017

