### **3.2 Secondary Objectives**

The secondary objectives of Aim 1 are to assess the effects of the performance improvement program on pain and individual BPSDs in the PWD, and the use of antipsychotic and analgesic. They will be measured at all four time points (0, 15, 30, and 60 days). BPSD will be measured using the NPI-Q. The type of pain assessment administered to the PWD will depend on their level of cognitive impairment. The level of impairment will be determined by the Quick Dementia Rating System (QDRS) score. The PWD who obtains a score of  $\leq 12$  will receive the Brief Pain Inventory Short Form^103 and those whose score  $\geq 12$  on the QDRS will receive the PAINAD which will be used to measure pain at rest and with movement. All PWD subjects will be assessed for pain during each visit using the respective measure.

The secondary objectives of Aim 2 are to assess the effects of the performance improvement program on informal caregiver burden, depression, and functional health and well-being. The PHQ-9 will be used to measure caregiver depression, the Zarit Burden Interview for caregiver burden and the SF-12 for caregiver health at 0 and 60 days.

The secondary objectives of Aim 3 are to assess the effects of the performance improvement program on the number of outpatient visits and contacts with the primary care provider. These will be measured through interviews at 30 and 60 days with the Resource Utilization Inventory.

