## 10.4 Description of Statistical Methods

### 10.4.1 General Approach

Data Analysis will be performed using SAS 9.4. We will perform statistical tests to examine baseline differences between the quality improvement program and control groups. We will then perform unadjusted comparison of both primary outcomes (patient and caregiver quality of life, emergency room visits) and secondary outcomes (pain, BPSD, delirium, caregiver depression burden, and burnout, hospital and emergency room admissions) between groups. We will focus on the endpoint measure for quality of life, and 30 and 60-day outcomes for emergency room utilization. For primary and secondary outcomes, we will perform a time trend analysis using a mixed effects linear model (PROC MCM). Mixed effects regression is used to analyze longitudinal data with repeated measures accounting for intra-individual and group clustering. We intend to use multivariate mixed effects regression modeling as opposed to traditional linear modeling or ANOVA in order to control for unobservable confounding variables that are constant over time but differ across PWD and/or caregivers. For both primary and secondary outcomes, we will then repeat the above analyses adjusting for baseline variables as covariates for a more efficient measurement of the effects of the quality improvement program. We will also perform correlation analyses to explore the relationship between pain and BPSD, and PWD and caregiver QOL through plotting scores over time and then if a significant correlation is present through adding to our mixed effect model. For utilization data, we will perform logistic regression to examine whether the patient is more or less likely to have a hospitalization or ER visit compared when receiving the quality improvement program at 30 and 60 days. We will then perform a Poisson Count Regression to compare the total number of hospitalizations and ER visits at each timepoint. In these models we will utilize a random effect to measure for clustering.

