**Table 2. Variables and Timing of Data Collection from PWD-Caregiver Dyads**

Variable	Instruments or Measures	Items	Min.	Timing of Data Collection (Days)							
				Patient				Caregiver			
				0	15	30	60	0	15	30	60
Consent				✓				✓			
Patient-Centered Outcomes											
Stage of Dementia	Quick Dementia Rating Scale 	10	5					✓			
BPSD	Neuropsychiatric Inventory Questionnaire	13	5					✓	✓	✓	✓
Quality of life	Quality of Life in Alzheimer's Disease 	13	5					✓			✓
Pain	Brief Pain Inventory Short Form	9	5	✓	✓	✓	✓				
Pain	PAINAD	5	3	✓	✓	✓	✓				
Patient Satisfaction	HHCAHPS	32	7						✓	✓	✓
Pain	Analgesic use (collected by RA on each dyad visit)	1	1					✓	✓	✓	✓
BPSD	Antipsychotic use (collected by RA on each dyad visit)	1	1					✓	✓	✓	✓
Delirium	FAM-CAM 	11	3					✓	✓	✓	✓
Caregiver Centered Outcomes											
Quality of Life	Caregiver Targeted Quality of Life 	80	20					✓			✓
Depression	Public Health Questionnaire 9 	9	3					✓			✓
Burden	Zarit Burden Inventory 	22	10					✓			✓
Health	SF-12 	12	3					✓			✓
Utilization Outcomes											
Healthcare Utilization	Resource Utilization Inventory 	13	5					✓		✓	✓
Sociodemographics											
Sociodemographics	Date of birth, sex, education, race, ethnicity	6	4	✓				✓			
Language, Religion and Culture	Primary language, religion, literacy (SAHL-SE) 	3	3	✓				✓			
Supports											
Social Support	Marital status, household members	2	<1	✓					✓		
Other unpaid caregivers	# individuals, # visits, #hrs/week	3	1	✓	✓	✓	✓	✓			
Paid Caregiver	# visits, hrs/week	2	1	✓	✓	✓	✓	✓			
Home nurse visits	# visits (chart)	1				✓	✓				
Physical/occupational therapy	# visits (chart)	2				✓	✓				
COVID-19 Effects on Caregiving	University of Pittsburgh COVID Caregiving Questionnaire and Investigator Derived from the Resource Utilization Inventory	18	6						✓		
Health and Functional Status											
Functional Status	Katz Activities of Daily Living  , Lawton Instrumental Activities of Daily Living 	12	2	✓	✓	✓	✓				
Comorbidities	Charlson comorbidity Questionnaire  (chart for patient, interview for caregiver)	17	3	✓					✓		

CONFIDENTIAL

This material is the property of the NYU School of Medicine and Langone Medical Center. Do not disclose or use except as authorized in writing by the study sponsor

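### Section 10.5 gives trend-model power for four observations, but both QOL primaries are measured twice; 345 enrolled allows 13.0% loss, not the stated 15%; and two recruitment stops conflict

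*Combined protocol and SAP*

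**What the plan says.** **Power.** Section 10.5 makes two statements, both at delta .45. The first is a two-sample comparison of QOL-AD at 60 days: 20 clusters of 15 dyads, ICC .05, power .80, alpha .05, with "covariates that account for a cumulative 15% of the variance in outcome". The second is for the mixed model, unadjusted, "assuming 15 dyads per cluster, 20 clusters, 4 observations, and an ICC = .05"; it names no outcome. Section 10.5 then treats the unadjusted detectable effect as an upper bound for adjusted analyses.

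**Where the model applies.** Protocol Summary: "Time trend analysis using repeated measure multivariate mixed effects linear models (PROC MCM in SAS) for all non-utilization outcomes". Section 10.4.1: "For primary and secondary outcomes, we will perform a time trend analysis using a mixed effects linear model (PROC MCM". Section 10.4.1 also says "We will focus on the endpoint measure for quality of life, and 30 and 60-day outcomes for emergency room utilization", and repeats the analyses "adjusting for baseline variables as covariates for a more efficient measurement" without naming those variables.

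**Schedule.** Sections 7.2.2 and 7.2.5 list QOL-AD and CGQOL at visits 1 and 4. Visits 2 and 3 list only the ADL/IADL items attached to the QOL-AD. In Table 2, the rows for QOL-AD and "Caregiver Targeted Quality of Life" are ticked at days 0 and 60 only. Of pain, individual BPSDs and medication use, section 3.2 says: "They will be measured at all four time points (0, 15, 30, and 60 days".

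**Loss and recruitment.** Sections 10.5 and 5.7.2 allow 15% loss and recruit 345 dyads for 300. Section 5.6 gives 207, 86 and 52 enrolled for 180, 75 and 45 complete, and ends recruitment at about 345 enrolled. Section 10.5 recruits until every cluster has 15 completers, and section 8.8.2 replaces withdrawals with completed cases.

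**The concern.** The four-observation sentence follows directly on the QOL-AD calculation, and the model it describes is the one assigned to the primaries. A reader will take it as power for the QOL trend analysis, which it cannot be. The power of a two-visit trend depends on the baseline to day-60 correlation and on the ICC of the change score, and the documents give neither.

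The loss allowance and the enrolment target do not agree with each other, and the two stopping rules end recruitment at different points. Section 10.1 says no formal SAP will be written, so section 10 is where these points have to be settled.

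**Working it through.** **1. Reproducing the 60-day figure.** Inputs from section 10.5: J = 20 clusters, m = 15, ICC = .05, delta = .45 SD, alpha = .05 (taken as two-sided).

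Variance of the difference = 4[ICC + (1 - ICC)/m]/J = 4(.05 + .95/15)/20 = .02267, so SE = .1506.
Noncentrality = .45/.1506 = 2.99. Noncentral t on 18 df gives **power .807**; the effect detectable at .80 is **.446**.

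With R2 = .15 (17 or 18 df):

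| Variance removed | Power at .45 | Detectable effect |
|---|---|---|
| Cluster level only | .830 to .833 | .431 to .433 |
| Both levels | .863 to .865 | .411 to .413 |

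So .45 is the no-covariate result. It is conservative for the covariate case it is attached to, in line with the upper-bound remark.

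**2. Four visits against two.** The documents give no within-person correlation, so the four-observation delta cannot be reproduced. As an illustration, assume compound symmetry with correlation r and unit SD. The variance of an estimated 60-day linear change is 2(1 - r) x 3600/(2 x S), where S is the sum of squared deviations of the visit days:
- days 0, 60: S = 1800, variance 2(1 - r);
- days 0, 15, 30, 60: S = 1968.75, variance 1.829(1 - r).

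Two-visit power at delta .45, 18 df:

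| Assumed change-score ICC | r = .3 | r = .5 | r = .8 |
|---|---|---|---|
| 0 | .88 | .96 | 1.00 |
| .025 | .77 | .89 | 1.00 |
| .05 | .67 | .81 | .99 |

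Over this grid, going from four visits to two costs 0 to 4 points. The level depends on how cluster variance enters: adding it on top of the person-level variance gives .644 and .787 at r = .3 and .5, instead of .666 and .807. Read the table as a range.

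**3. Naming baseline QOL.** In the day-60 model, multiply the variance at both levels by (1 - r squared), on 17 df: power .839, .902 and .997 at r = .3, .5 and .8, against .807 unadjusted. If baseline explains only within-team variance (18 df): .826, .861 and .941. Since the square root of .15 is .387, it improves on the plan's own R2 = .15 allowance only if r exceeds about .39. Strata use up degrees of freedom: with 10 df left and r = .3, power is .806, no better than unadjusted.

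**4. Loss.** 300 x 1.15 = 345. Loss allowed: 1 - 300/345 = 13.0%. At 15% loss, 345 x .85 = 293.25, and 300 completers need 300/.85 = 352.9, about 353. By site, 207, 86 and 52 x .85 = 176, 73 and 44, not 180, 75 and 45.

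Power at 293.25/20 = 14.66 per cluster: .802 if clusters are equal. With design effect 1 + [(1 + CV squared) x 14.66 - 1] x .05, an assumed cluster-size CV of .1, .2 or .3 gives .800, .795 or .787.

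**5. Do the two stops coincide?** Spread 345 as 15 clusters of 17 and 5 of 18 (255 + 90) and assume independent losses. The chance that all 20 clusters reach 15 completers is about .00001 at 15% loss and .0002 at 13%.

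**The case against.** The best defence is that little turns on this. The calculation that names the primary does not use the visit count, section 10.4.1 puts the QOL focus on the endpoint measure, and the four-observation sentence names no outcome. All of that stands. A reader might infer that the trial is underpowered for QOL or that N = 300 is invalid; the documents support neither.

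The delta .45 wording is also largely answered by section 10.5's own upper-bound remark. What remains is a conservative mismatch.

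On recruitment, section 5.6 says approximately 345 and gives 300 evaluable dyads as the purpose, so the intent is visible. But a total enrolment cannot secure 15 completers in each of 20 teams, and the text does not say which rule prevails.

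Naming baseline QOL could be called a preference, since section 10.4.1 already adjusts for baseline variables and models clustering. Its gain is indeed conditional on r. It remains worthwhile because the measure is already collected and the covariates are otherwise unspecified.

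It would also be wrong simply to hand the four-observation figure to every four-visit outcome. Pain is split between BPI and PAINAD by QDRS score, so neither instrument supplies 15 dyads per cluster, and medication use is a one-item variable. Delta .45 is not shown to fit these.

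**Conclusion.** The point holds as a set of corrections, not as a power failure. The four-observation statement does not describe the QOL-AD or CGQOL trend model. The 60-day QOL-AD comparison stands at .807 unadjusted and .83 to .87 with the stated covariates.

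The target of 345 matches 13.0% loss. At 15% about 293 complete, which costs about half a point of power with equal clusters (.802). Unadjusted power slips just under .80 (.795 to .787) at an assumed size CV of .2 to .3, so .80 is not guaranteed at 293. The stopping conflict is real, and the documents do not resolve it.

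The schedule mismatch and the loss arithmetic rest on the documents alone. The trend-power range, the size of any baseline-adjustment gain and the unequal-cluster figures rest on assumed values of r, change-score ICC and CV. One caveat: the visit lists attach a QDRS condition of 12 or less to QOL-AD. Section 3.1 and Table 2 point to caregiver rating, so the condition may not reach the primary; the figures here assume that it does not.

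**What to change.** - **Section 10.5, trend model:** state that the four-observation figure does not apply to QOL-AD or CGQOL, and name the continuous four-visit outcome it is meant for. Do not extend it to split-instrument pain or one-item medication use without separate justification.
- **QOL power:** base it on the day-60 comparison, and say whether .45 is the no-covariate or the R2 = .15 result. Give any two-visit trend power only as a range over assumed correlation and change-score ICC.
- **Section 10.4.1:** prespecify baseline QOL as a covariate in the day-60 QOL-AD and CGQOL models, with a care-team random effect, and agency as a stratum where degrees of freedom allow.
- **Sections 5.6, 5.7.2 and 10.5:** say either that 345 allows 13.0% loss or that 15% loss gives about 293 completers, and correct the site lines to match.
- **Recruitment stop:** say which rule governs. The 345 cap needs no extra enrolment but accepts fewer than 300 completers at 15% loss. The rule of 15 per cluster implies about 353 or more enrolled at that loss.

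The power, loss and stopping edits are wording and recalculation. The covariate choice is an analysis-plan change that needs no new data and should be fixed before the final unblinded comparison. Enrolment rises only if the completer rule is chosen.
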